#### 9.1.2.3. Identification and Treatment of MS Relapse

A relapse is defined as the occurrence of new or worsening neurological symptoms attributable to MS and immediately preceded by a relatively stable or improving neurological state of at least 30 days. The new or worsening neurological symptoms must be accompanied by objective neurological worsening, based on examination by the blinded evaluator, consistent with an increase of at least half a point on the EDSS, or 2 points on one of the appropriate Functional System (FS) scores, or 1 point on two or more of the appropriate FS scores.

The change in FS scale scores should correspond to the patient's symptoms (e.g. patient reported change in visual acuity should correspond to a change in the vision FS score). Symptoms must persist for > 24 hours and should not be attributable to confounding clinical factors (e.g., fever, infection, injury, adverse reactions to concomitant medications). EDSS and FS scores documented by the blinded evaluator at the time of the relapse will be verified by that the treating investigator who will determine whether change in EDSS and FS scores meet the protocol defined relapse definitions and determine whether relapse treatment will be administered.

When a patient experiences new or worsening symptoms that may indicate a possible relapse, he/she should telephone the treating investigator within 48 hours of symptoms onset. The treating investigator will conduct a telephone questionnaire and, as necessary, will arrange an unscheduled relapse assessment visit. The treating physician will then assess whether the

symptoms had onset in the presence of fever or infection. If fever or infection can be excluded, a neurological examination by the independent evaluating physician must be arranged as soon as possible, preferably within 7 days of the onset of symptoms. The blinded evaluator should perform the EDSS, and the blinded evaluator or blinded MSFC assessor should perform the MSFC and LCLA.

If no neurological worsening is observed, the patient will continue to attend the next scheduled study visit.

If a non-MS related disease is suspected, the treating investigator should perform additional assessments to determine the cause of worsening. The Medical Monitor should be contacted as needed to discuss any question regarding eligibility for further treatment or study participation.

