#### 5.4.3. Visit Windows

A visit window method will be applied to determine visits across the study for MRI efficacy parameters and for the minimum times to confirmation of disability progressions. For MRI parameters, if a patient has multiple assessments within a visit window the value closest to the target day for that visit will be selected. If there are two values which are equidistant in terms of time then the later value will be selected. For disability progressions, a minimum length of time since the start of the progression is defined, based on the low end of the MRI visit window specifications.

The following visit windows are defined for MRI parameters:

Visit	Target Day	Window
Month 6	180	166 - 194
Month 12	360	346 - 374
Month 18	540	526 – 554
Month 24	720	706 - 734

The following minimum times are defined for disability progression confirmations:

- 3 month confirmation:  $\geq$  76 days after start of progression
- 6 month confirmation: ≥ 166 days after start of progression

For all efficacy and safety parameters, the last available assessment will be derived as the last value on treatment, whether scheduled or unscheduled.

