### Sustained Disability Progression

Sustained disability progression is defined as at least a 1.0 point increase on the EDSS score from Baseline, confirmed after a 3 month and a 6 month period. Confirmation of MS disease progression must not occur at the time of a relapse. If the patient is scheduled to be evaluated to confirm disability at the time of a relapse, the disability event must be assessed at a later visit, which may be the next scheduled visit, or at an unscheduled visit conducted after the relapse has resolved. The date of the initial visit at which the minimum increase in the EDSS is met will be the date of onset of the progression (tentative progression).

Disability progression can be confirmed at the early withdrawal visit, according to the rules above, as long as the early withdrawal visit is not also a relapse assessment visit.

Death due to MS will be counted as a confirmed progression. If the patient was in the midst of a tentative progression at the time of death, the progression date will be the date of the start of the progression. Otherwise, the progression date will be the date of death.

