The MSFC z-score is calculated by creating z-scores for each component of the MSFC, as explained below, and averaging them to create an overall composite score, i.e.,

MSFC z-score = 
$$(Z_{25\text{-foot-walk}} + Z_{9HPT} + Z_{SDMT})/3$$
, and

MSFC z-score (LCLA) =  $(Z_{25\text{-foot-walk}} + Z_{9\text{HPT}} + Z_{SDMT} + Z_{LCLA})/4$ , where  $Z_{xxx}$  refers to Z-scores

A z-score represents the number of standard deviations a patient's test result is higher (z > 0) or lower (z < 0) than the average test result (z = 0) of the reference population.

The following describes the scoring, and rules for missing value imputation for each component.

Timed 25-Foot Walk Z-score Calculation

The Z-score is calculated as in the following formula:

$$Z_{25\text{-foot-walk}} = (-1) * \frac{((t_1 + t_2)/2) - MEAN(reference)}{SD(reference)}$$

where  $t_1$  and  $t_2$  are the time (in seconds) from the two trials, and the mean (reference) and SD (reference) are the mean and standard deviation respectively, of baseline values for the reference population. The reference population will be the study population.

For missing post-Baseline values, if a patient is missing only one trial for any post-Baseline visit, then the score from the non-missing trial will be used to calculate the Z-score. The steps outlined above will remain the same except the actual times will not be averaged.

The missing data algorithm suggested by the MSFC manual will be used to impute missing values. If both scores from the two trials are missing for any post-Baseline visit, due to MS related physical limitation or other physical limitations, then the patient will be given a Z-score of -13.7 for the Timed 25-Foot walk. If the reasons for missing scores on both trials are due to other reasons (non-compliance, missed visits), then LOCF from post-Baseline values will also be used as to impute the z-score for that visit. If a value is not available to carry forward, the mean of the available z-scores using all available data from the same treatment group, will be calculated at the specified visit and used as the imputed value. Values imputed using the mean will not be carried forward to other visits.

If a patient has missing data at Baseline for either trial, then the mean of the available z-scores will be evaluated by treatment group and used as the imputed value.

9HPT Z-score Calculation

Z-score for the 9HPT is calculated as in the following formula:

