#### SDMT Z-score Calculation

For the SDMT, the z-score for each patient at each time-point will be created by subtracting the reference population's baseline mean score on the SDMT from the patient's SDMT score and dividing by the baseline SD on the SDMT of the reference population, i.e.

$$Z_{SDMT} = \frac{SDMT \text{ raw score} - MEAN(reference)}{SD(reference)}$$

and SDMT raw score = # of correct items within the timeframe of the test. The reference population will be the study population.

For missing post-Baseline values, if a patient is missing the SDMT score due to MS related physical limitation or other physical limitations, then a score of 0 will be assigned. If the reasons for missing score is due to other reasons (non-compliance, missed visits), then LOCF from post-Baseline values will also be used as to impute the z-score for that visit. If a value is not available to carry forward, the mean of the available z-scores using all available data from the same treatment group, will be calculated at the specified visit and used as the imputed value. Values imputed using the mean will not be carried forward to other visits.

The change from Baseline in the MSFC scores and the actual values at each visit will be summarized in each treatment group. The changes in MSFC scores at Month 24 will be analyzed and compared between treatment groups using an ANCOVA model adjusting for region, EDSS category at Baseline, and the Baseline MSFC score.

LCLA is performed with standardized set of charts (Sloan charts or Tumbling E charts) to assess low contrast visual acuity. Each chart corresponds to a different contrast level, and charts are scored according to the number of letters that are identified correctly.

Change from Baseline in visual function test scores as assessed by LCLA will be summarized by treatment group and time point, and will be compared at Month 24 between treatment groups using ANCOVA adjusted for region, EDSS category at Baseline, and the Baseline visual function test score.

### Secondary Endpoint: Change in MSQOL-54 score from Baseline to Month 24

Actual scores and change from Baseline by visit will be summarized for each of the 12 subscales, the 2 summary scores, and the 2 single-item measures shown below:

- Subscales
  - 1. Physical function
  - 2. Role limitations physical
  - 3. Role limitations emotional
  - 4 Pain
  - 5. Emotional well-being
  - 6. Energy
  - 7. Health perceptions
  - 8. Social function
  - 9. Cognitive function

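### The MSFC carry-forward rules in the SAP do not keep out scores taken at a relapse visit, so an acute-relapse score can stand in for a missing Month 24 component

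*SAP*

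**What the plan says.** **When the MSFC is measured.** After baseline, Protocol Table 3 schedules it at Months 6, 12, 18 and 24. Table 4 and Section 10.4 add it at every Unscheduled Relapse Visit. Section 9.1.2.3 says of that visit that "the blinded evaluator or blinded MSFC assessor should perform the MSFC and LCLA", with the examination timed "preferably within 7 days of the onset of symptoms". Table 4 and Section 10.5 also place it at the Early Termination visit.

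**Which value counts as last.** SAP 5.4.3 defines visit windows only for MRI and minimum times only for confirming progression. For everything else, "the last available assessment will be derived as the last value on treatment, whether scheduled or unscheduled".

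**How missing components are filled.** In SAP 9.3.1, if a walk, peg or SDMT score is missing for reasons such as non-compliance or a missed visit, "then LOCF from post-Baseline values will also be used as to impute the z-score for that visit". The only stated limit on what may be carried is "Values imputed using the mean will not be carried forward to other visits". If both walk trials are missing at a post-Baseline visit because of physical limitation, "then the patient will be given a Z-score of -13.7 for the Timed 25-Foot walk". The peg test (777 seconds) and SDMT (score 0) have their own fixed penalties.

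**Where relapse is guarded against.** For EDSS progression, SAP 9.2.1 states: "Confirmation of MS disease progression must not occur at the time of a relapse". It also bars confirmation at an early withdrawal visit that doubles as a relapse assessment. Protocol 11.1.1 delays MRI until 30 days after methylprednisolone given for a relapse. No such guard exists for the MSFC.

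**The concern.** The MSFC serves the objective on accumulation of disability, so the Month 24 score should describe function after two years. A score taken within days of relapse onset describes an acute loss that may be temporary. These extra measurements exist only in patients with a suspected relapse, and the trial is planned on the expectation of more relapses on IFN β-1a. If they can fill a missing Month 24 value, the arm with more relapses is marked down for the timing of its last measurement as well as for lasting disability.

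The penalty scores raise the stakes. A patient who cannot walk at a relapse visit gets -13.7 on that component, which is -13.7/3 = -4.57 on the three-part composite, and nothing bars carrying it. SAP 9.3.1 plans no MSFC sensitivity analysis that would reveal this. Because the LOCF text does not mention unscheduled visits, two programmers could also derive different Month 24 values from the same data.

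**Working it through.** **Planning inputs.** Neither document gives a figure for MSFC imputation, so the relapse and dropout rates come from the sample-size sections. As a check on those inputs:

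n per arm = σ² (z₁₋α/₂ + z_power)² [1/(λ₁t) + 1/(λ₂t)] / [ln(λ₂/λ₁)]², with σ² = 1.3 and two-sided α = 0.025.

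- SAP 5.1 (0.30 vs 0.17, t = 1 year, 80% power): 352.98, so 353 as stated.
- Protocol 13.2 (0.30 vs 0.19, t = 2 years, 90% power): 332.4, so 333 as stated.
- Dropout: 353/0.88 and 333/0.83 both round up to 402, in line with about 400 per arm.

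**Assumptions.** Relapses follow a Poisson process and each produces one relapse visit. Withdrawal is unrelated to relapse. The planned dropout (12% in the SAP, 17% in the protocol) stands in for a missing Month 24 MSFC. No Early Termination value exists.

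**Step 1: chance that the newest MSFC is a relapse-visit value.** The gap between scheduled assessments is 0.5 year. If only Month 24 is missed, the chance is 1 − exp(−0.5λ). If dropout is spread evenly over a gap, it is 1 − [1 − exp(−0.5λ)]/(0.5λ).

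| Pattern | IFN, 0.30 | RPC1063, 0.19 | RPC1063, 0.17 |
|---|---|---|---|
| Even dropout in the gap | 0.0714 | 0.0460 | 0.0413 |
| Only Month 24 missed | 0.1393 | 0.0906 | 0.0815 |

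**Step 2: share of the whole arm.**

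- IFN: from 0.12 × 0.0714 = 0.86% to 0.17 × 0.1393 = 2.37%, or 3.4 to 9.5 of 400.
- RPC1063: from 0.12 × 0.0413 = 0.50% to 0.17 × 0.0906 = 1.54%, or 2.0 to 6.2 of 400.
- Gap between arms: from 0.12 × (0.0714 − 0.0460) = 0.00305 to 0.17 × (0.1393 − 0.0815) = 0.00983, which is 0.3 to 1.0 percentage points.

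**Step 3: bias in the difference of mean Month 24 MSFC.** The documents do not say how much lower a relapse-visit score is. I assume 0.5 to 1.0 z on the composite.

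- Ordinary case: 0.5 × 0.00305 = 0.0015 to 1.0 × 0.00983 = 0.0098 z.
- If every carried score included the walk penalty: 4.57 × 0.00305 = 0.014 to 4.57 × 0.00983 = 0.045 z.

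**Step 4: extreme clustering.** Suppose every dropout who would relapse within 24 months leaves at that relapse. The chances become 1 − exp(−2λ): 0.451 for IFN, and 0.316 (ARR 0.19) or 0.288 (ARR 0.17) for RPC1063.

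- Shares: 5.4-7.7% of IFN and 3.5-5.4% of an RPC1063 arm.
- Gap: 0.12 × (0.451 − 0.316) = 1.6 to 0.17 × (0.451 − 0.288) = 2.8 points.
- Bias: 0.008 to 0.028 z, or 0.07 to 0.13 z if the walk penalty is carried every time.

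**The case against.** **The link is inferred.** SAP 9.3.1 does not cite the last-available rule in 5.4.3 and does not mention unscheduled visits, so a reader should not infer that the SAP instructs the use of relapse scores. That stands. But the text permits it, 5.4.3 points that way, and an open choice should be closed before unblinding.

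**Early Termination values usually come later.** Protocol 9.4.4.1 asks everyone who stops medication to attend that visit, and it includes the MSFC. This stands and makes the shares above upper-side figures for each scenario. It does not close the gap: some patients will not attend, the visit may itself be a relapse assessment, and the on-treatment wording in 5.4.3 may exclude a value taken after the last dose.

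**LCLA.** A reader might extend the point to the low-contrast acuity test, which is also done at relapse visits. The documents do not support that. For LCLA the SAP says only "Change from Baseline in visual function test scores as assessed by LCLA will be summarized by treatment group and time point", followed by a Month 24 ANCOVA. It states no LOCF rule.

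**SDMT.** The SAP scores SDMT as the third MSFC component, but the protocol names PASAT-3 (Section 11.1.4) and lists SDMT at no visit. A relapse-visit score is therefore established only for the walk and peg tests.

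**The EDSS comparison is partial.** SAP 9.2.1 bars confirmation at a relapse, but a relapse-visit EDSS may still start a tentative progression. The SAP guards one step and does not discard such values generally.

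**Direction.** It is tempting to say that the bias always favours RPC1063. That requires IFN to relapse more, as planned, and dropout, reasons for missingness and relapse severity to be alike across arms. The documents give none of these by arm.

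**Conclusion.** The gap is real for the MSFC and small in the ordinary case. When Month 24 is missing for non-physical reasons, and there is no later scheduled or Early Termination value, an acute-relapse component score or a penalty score assigned at that visit can be carried to Month 24. The share affected is about 0.9-2.4% of the IFN arm and 0.5-1.5% of an RPC1063 arm, before Early Termination values reduce it. The bias is about 0.002-0.010 z toward RPC1063, given the planning rates and the assumed 0.5 to 1.0 z deficit.

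It grows only if withdrawals cluster at relapses or penalty scores are carried. Clustering is plausible, because Protocol 9.1.2.3 requires a discussion of alternatives and re-consent after each relapse, but the documents do not quantify it. The 0.07 to 0.13 z figures need both conditions at their limit and are not a forecast.

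The 14% versus 9% from Step 1 should not be read as shares of the arms; they apply only to patients who were seen at Month 18 and then missed Month 24. Nor does the point threaten the main results: the MSFC is an other secondary endpoint without multiplicity adjustment (SAP 5), and the primary and key secondary analyses are untouched. The change is still worth making because the bias is avoidable and cheap to remove.

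**What to change.** In SAP 5.4.3 and 9.3.1, add that for MSFC components no value or fixed penalty score from an Unscheduled Relapse Visit, or from an Early Termination visit that is also a relapse assessment, may be carried forward or serve as the last available assessment. Carry the last other post-Baseline value instead, whether from a scheduled visit or a non-relapse Early Termination visit, and name the latter explicitly so that the on-treatment wording does not remove it. Keep the excluded values in the listings. If an LCLA imputation rule is added later, apply the same exclusion.

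This costs one sentence and one programming flag, and it brings the affected share to zero in every arm. The downside is that a few patients will carry an older value, which may miss some genuine worsening, or will fall back on the treatment-group mean.

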#### 5.4.4. Missing and Partial Data

Missing data may be imputed for some efficacy endpoints as described in the following sections. For partial dates, the algorithms for imputation will vary depending upon the parameter; the details can be found in Appendix A Imputation Algorithm for Partial and Missing Dates.

### 6. PATIENT DISPOSITION

A summary of disposition of patients will include the number and percentage of patients for the following categories: patients screened, patients randomized, patients treated (safety population), patients in the ITT population, patients in the PP population, patients completing the study, and patients discontinued from the study. All percentages will be based on the number of patients randomized.

The reasons for study discontinuation will also be summarized in this table. The reason for discontinuation may include any of the following: adverse event, death, lost to follow-up, withdrawal of consent, or other. Only one reason for study discontinuation will be recorded. For patients lost to follow-up, the number of days until lost to follow-up will also be presented using descriptive statistics. The number of days until lost to follow-up

on study is defined as the number of days from randomization until the date of last contact.

A listing will present data concerning patient disposition.

# 7. DEMOGRAPHICS, MEDICAL HISTORY AND BASELINE CHARACTERISTICS

### 7.1. Demographics

The demographics and baseline characteristics will be presented in tables. The demographic characteristics consist of age, age category, sex, race, ethnicity, weight, weight category, height, body mass index, and region. A patient's age in years is calculated using the date of the informed consent and date of birth, or recorded directly on the eCRF. Age will be summarized using the descriptive statistics. The number and percentage of patients in each age category (18-19, 20-29, 30-39, 40-49, 50-55, and >55, as well as <40, ≥40), and in each race category (White, Black, Asian, American Indian or Alaska Native, Native Hawaiian or Other Pacific Islander, and Other) will be reported. The demographics and baseline characteristics summaries will be presented for both ITT and PP populations.

Demographics and baseline characteristics data will be listed.

### 7.2. Medical History

### 7.2.1. General Medical History

Medical history data other than for MS will be presented in a table. The table summary will show the number and percentage of patients with a significant history for each body system. Percentages will be calculated out of the number of patients in the Safety population. Significant medical history including specific details will be listed.

### 7.2.2. Multiple Sclerosis Disease History

Multiple sclerosis disease history will be summarized for the ITT population using the descriptive statistics for the following parameters:

- EDSS score at Baseline
- EDSS category at Baseline
- Age at MS symptoms onset
- Age at MS diagnosis
- Years since MS symptoms onset
- Years category since MS symptoms onset
- Years since MS diagnosis
- Years category since MS diagnosis

- Number of relapses within the last 12 months prior to screening
- Number of relapses within the last 24 months prior to screening
- Number of GdE lesions at Baseline
- T2 lesion volume at Baseline

In addition to reporting the summary statistics, the following duration categories will be used for selected continuous parameters: For the years since MS symptom onset and years since MS diagnosis: 0 - <1, 1 - <2, 2 - <5, 5 - <10, 10 - <15,  $\ge 15$ . EDSS score at Baseline: 0 - 2, 2.5 - 3.5, 4 - 5, >5. Number of relapses within the past 12 and 24 months: 0, 1, 2-3, >4. Number of GdE lesions at Baseline: 0, 1, 2, 3, >4.

MS history data will be presented in a listing. Incomplete diagnosis dates will be imputed as detailed in Appendix A.

### 7.3. Inclusion and Exclusion Criteria

The details of Inclusion and Exclusion criteria are listed in Section 9.4.1 and 9.4.2 of the protocol.

The protocol deviations/violations will be summarized and presented in a listing.

### 8. TREATMENTS AND MEDICATIONS

#### 8.1. Prior and Concomitant Medications

All treatments being taken by the patients on entry to the study or at any time during the study in addition to the investigational product are regarded as concomitant treatments and must be documented on the appropriate section of the eCRF. A history of all prior medications will be documented to at least 4 weeks prior to study participation, and a history of previous treatments for MS will be documented for the prior 2 years. All medications will be coded with the WHO Drug dictionary.

Prior and concomitant medications will be summarized by drug class and preferred term. At each level of summarization, a patient is counted once if he/she reports one or more medications at that level. Prior and concomitant medications will be sorted by descending incidence within each drug class in the total RPC1063 group.

Prior medications are defined as medications with a stop date occurring before the first dose date. Concomitant medications are defined as medications that are ongoing at the first dose date or with a start date occurring on or after the first dose date. Medications with start and stop dates which bracket the first dose date will be summarized as concomitant medications. Medications will be defined as prior or concomitant, but not both. If based on start and stop dates it cannot be determined whether a medication is prior or concomitant, then it will be considered concomitant.

Prior medications used to treat MS will also be summarized separately.

All prior and concomitant medications will be presented in a listing.

